RESEARCH PROTOCOL

Official Title: Effects of AINurse Orientation Program on Psychological Outcomes and Length of Hospital Stay: A Randomized Controlled Trial

Date of the document: September 1, 2025

Method

Aim

This study aimed to develop a structured AINurse and Human Nurse orientation training program for intensive care unit (ICU) patients and compare the effects of these training programs on ICU patients' delirium-free days, level of anxiety and depression, and length of stay in the ICU.

Study Type and Design

This study is designed as a single-center, randomized controlled experimental study. The study trial protocol will be registered on clinicaltrials.gov . The Consolidated Standards of Reporting Trials (CONSORT) diagram will be used for reporting the study.

Hypotheses of the Study

H1: Patients who receive the structured AINurse patient orientation training program will have longer delirium-free days than patients who receive Human Nurse orientation training.

H2: Patients who receive the structured AINurse patient orientation training program will have lower levels of anxiety and depression than patients who receive the Human Nurse orientation training.

H3: Patients who receive the structured AINurse patient orientation training program will have shorter lengths of stay in the intensive care unit than patients who receive the Human Nurse orientation training.

Setting, Participants, and Sample Size

The study is planned to be conducted between July 2025 and July 2026 in the adult intensive care unit of Koç University Hospital, a tertiary care hospital in Türkiye. The general intensive care unit (GICU) of Koç University Hospital has 16 beds and the cardiovascular surgery intensive care unit (CVSICU) has eight beds. The hospital where the study will be conducted has a total of 1950 patient admissions annually, 1500 in the NICU, and 450 adult patients in the CVSICU. While the experimental group will receive the AI Nurse Orientation Training Program, the control group will receive the Human Nurse Orientation Training Program. Since there is no similar study to this study, a pilot study will be conducted with 10 patients. After the pilot study, the sample size will be calculated using G-Power.

The inclusion criteria of the participants in the study included (1) intensive care unit confusion assessment scale (CAM-ICU scale) score of 0-2, (2) age 18 years or older, (3) hospitalized in the intensive care unit for at least 24 hours, (4) Glasgow coma scale score of 13-14-15 points, (5) RASS score between -1 and +1, (6) no hearing problems.

Participants with any of these characteristics will be excluded: (1) intensive care unit confusion assessment scale (CAM-ICU scale) score of 6-7, (2) any psychiatric illness or impaired brain function, (3) defined hearing loss, (4) advanced dementia, (5) younger than 18 years of age, (6) RASS score outside the range of -1 to +1, (7) sedative medication, (8) history of surgery or disease around the ear.

Recruitment, randomisation, and blinding

To assign eligible participants to study groups, a computer-assisted simple randomization method will be employed. The randomization process will be performed by a statistical expert other than the researcher and will be forwarded to the researcher. For this, the website "<https://www.random.org/integer-sets>" will be used. This approach aims to minimize selection bias and control for potential confounding variables by ensuring equal probability of assignment to either the intervention or control group.

Study Intervention

The study consists of four stages.

Phase 1: Development of the Structured Orientation Program: Structured orientation training programs will be developed by the researchers for both AI Nurse and Human Nurse interventions based on the literature (Kasapoğlu et al.,2022; Ma et al.,2025). While the AINurse training program will be implemented in the experimental group, the Human Nurse training program will be implemented in the control group. The content of the structured training program for both groups will be the same (Appendix-2). The training content will be sent to the opinion of 10 experts who are experts in intensive care and AI, and changes will be made in the training program.

In the AINurse training program, the training text will be written in a patient-friendly language to enhance comprehensibility. The Narrative Orientation Experience model will be used not only to deliver information but also to support the patient's psychosocial adaptation to the intensive care environment. Within this method, key information such as time, place, care

environment, relatives, and daily routine will be presented in the form of a scenario format in a “starting the day story” in which the patient is addressed by name to foster a sense of personal connection and orientation.

Phase 2: Development of AI-Nurse orientation program/software: The AI-Nurse orientation program to be implemented in the intervention group will be developed by a researcher with expertise in AI and engineering, who is also part of the study team. During the development phase, the content of the program will be structured by the researchers to be compatible with individual patient information. Voice-based orientation training will be delivered using the Google Cloud Text-to-Speech (TTS) API, which enables the conversion of written text into natural-sounding speech.

The TTS engine allows for customization of voice parameters, including gender (female and male), speech tempo (slowed), and tone (calm). For Turkish language output, the use of 'tr-TR-Wavenet-A' or 'tr-TR-Standard-B' voice models is recommended. The training content can be personalized, with relevant information about the patient, weather, and family-related data will be automatically retrieved from the database. The AI Nurse system will be developed to work via mobile devices (e.g., an Android tablet). The patient will listen to the audio training through headphones and, if necessary, will be able to read the text on the screen.

The training program will include approximately 10 minutes of audio narration and will be administered twice daily over a period of three days. Existing orientation practices in the hospital will be observed and documented. During this observation, all elements of nurse-patient interaction, such as whether the nurse introduces herself/himself, whether she/he gives day information, and whether she/he provides information about the environment, will be detailed. The control group will receive a researcher-designed orientation training program of similar duration and frequency, comprising 10-minute sessions delivered over three consecutive days.

Phase 3: Piloting the AI-Nurse orientation training program: The developed AI-Nurse training program will be conducted as a pilot study with 10 patients hospitalized in the ICU. A sample calculation will be made as a result of the pilot study. Patients included in the pilot study will not be included in the sample.

Phase 4: Implementation of structured orientation training to intervention and experimental group: In the experimental group, the structured AI-Nurse orientation program will be listened to twice daily (10:00 and 14:00) through a headset connected to a structured

audio recording application. The content will include orientation to time and environment but will exclude any personally identifiable information such as the patient's name. Following each orientation session, the daily news will be played with the help of the television in the patient's room (at 10:30-14:30), aiming to enhance environmental awareness and perception of real-time audio streaming. The TTS engines to be used will be able to provide real-time audio streaming. This intervention will be implemented by the same researcher over a three-day period. Anxiety and depression levels, as well as the CAM-ICU score, will be assessed both before and after the intervention. After three days of structured AI-Nurse training, the patient's discharge time from the ICU will be followed and recorded. In the control group, the structured orientation training will be given face-to-face by the Human-Nurse researcher. The patient in this group will also be monitored for signs and symptoms of delirium for three days. Anxiety and depression levels will be measured prior to the intervention, while post-intervention evaluations will include the number of delirium-free days, anxiety and depression scores, and length of stay in the ICU.

Data Collection Instruments

Data will be collected using the sociodemographic characteristics form, a clinical patient information form, the Confusion Assessment Method-Intensive Care Unit (CAM-ICU), and the Hospital Anxiety and Depression Scale (HADS). In the initial stage, patients will be screened for the presence of delirium using the CAM-ICU. Following this, their sedation and agitation levels will be assessed using the Richmond Agitation Sedation Scale (RASS), and eligibility for study inclusion will be determined based on these scores. The RASS is a validated tool used to assess the level of sedation and agitation in patients admitted to intensive care units, with scores ranging from +4 to -5. Positive scores indicate increasing levels of agitation (e.g., +4: combative, +3: very agitated, +1: restless), while negative scores reflect deeper levels of sedation (e.g., -1: drowsy, -2: lightly sedated, -5:unarousable). A score of 0 indicates an alert and calm state (Sessler et al., 2002).

Sociodemographic information form: The sociodemographic information form developed by the researchers consisted of eight questions about name, age, gender, occupation, marital status, education, smoking, and alcohol use. (Appendix-1)

Clinical patient information form: It was created by the researchers from a total of 11 questions, including the patient's diagnosis, acute physiological and chronic health evaluation II (APACHE II) score, mean arterial pressure (MAP), blood urea nitrogen (BUN), metabolic

acidosis, use of analgesic drugs, use of physical restraint, infection, respiratory failure and corticosteroid use, and the presence of catheters/tubes in the patient. (Appendix-1)

Confusion Assessment Method for the Intensive Care Unit (CAM-ICU): This form will be utilized to assess the presence of delirium in critically ill patients. Originally developed by Ely et al. (2001) to facilitate the identification of delirium by nurses and physicians in intensive care settings, the Turkish validity and reliability of the scale were established by Akıncı et al. (2005), with a reported Cronbach's alpha coefficient of 0.96, indicating excellent internal consistency. The CAM-ICU evaluates four key features in critically ill patients: (1) acute onset or fluctuating course of mental status, (2) inattention, (3) altered level of consciousness, and (4) disorganized thinking. A positive diagnosis of delirium is made when the first two criteria are present, along with either the third or fourth. The scale yields a total score ranging from 0 to 7, with interpretive cut-off points as follows: 0–2 indicating no delirium, 3–5 suggesting mild to moderate delirium, and 6–7 indicating severe delirium (Akıncı ve ark.,2005). (Appendix-1)

The Hospital Anxiety and Depression Scale (HADS): This scale was developed by Zigmond and Snaith (1983) to assess the severity and risk of anxiety and depression in hospitalized patients. The Turkish validity and reliability study of the scale was conducted by Aydemir et al. (1997), reporting a Cronbach's alpha coefficient of 0.85, inter-item correlation coefficients ranging between 0.81 and 0.85, and a split-half reliability coefficient of 0.85, indicating strong internal consistency. The scale comprises 14 items in a 4-point Likert format. Odd-numbered items assess anxiety symptoms, while even-numbered items assess depressive symptoms. Items 1, 3, 5, 6, 8, 10, 11, and 13 are reverse scored (3, 2, 1, 0), while items 2, 4, 7, 9, 12, and 14 are scored progressively (0, 1, 2, 3). Subscale scores are obtained by summing the relevant items: questions 1, 3, 5, 7, 9, 11, and 13 for the anxiety subscale (HAD-A), and questions 2, 4, 6, 8, 10, 12, and 14 for the depression subscale (HAD-D). In the Turkish adaptation, the cut-off scores were identified as 10/11 for the anxiety subscale and 7/8 for the depression subscale. Scores exceeding these thresholds indicate a risk of clinically significant anxiety or depression (Yiğitoğlu et al., 2021). (Appendix-1)

Data Collection and Follow-up

Data collection will take place between July 2025 and July 2026. After obtaining written informed consent, randomization will be performed among patients hospitalized in the intensive care unit and the cardiovascular surgery intensive care unit who meet the inclusion criteria and voluntarily agree to participate in the study. In the first stage, patients' CAM-ICU form and RASS scores will be calculated. For patients who meet the inclusion criteria, the

sociodemographic characteristics form and clinical patient information form will be completed by the researchers. Patients in the intervention group included in the study will be given structured AI-Nurse orientation training starting at 10:00 am (approximately 10 minutes), and then the patient will listen to the daily morning news on television. At the end of the day, at 16:00, CAM-ICU and HADS will be evaluated. This process will continue with the same patient for three days. If the delirium score is between 3 and 7 points for three days and the RASS value is +4 belligerent, +3 very agitated, -2 slightly sedated, -3 moderately sedated, -4 deep sedation, -5 unstimulated, this training and follow-up process will be stopped, and the intervention will be ended. Patients assigned to the control group will fill in the same forms, and after the structured orientation training is given by the researcher (Human Nurse), the television will be turned on in the same way, and the daily news will be listened to. At the end of the day, CAM-ICU and HADS will be evaluated at 16:00. This practice will continue with the same patients for three days. After three days of follow-up, the length of stay of the patients in the intensive care unit will be monitored until discharge.

Data Analysis

Data will be analyzed using IBM SPSS Statistics, Version 28.0 (Armonk, NY: IBM Corp., 2021). Sociodemographic characteristics will be reported using descriptive statistics such as frequency, percentage, mean, and standard deviation. Descriptive statistics will be used to analyze the data. Whether the data are normally distributed will be evaluated with the Shapiro-Wilk test. The t-test will be used for normally distributed data. If the data are not normally distributed, the Mann-Whitney U test will be used.

Ethical Consideration

Ethical approval will be obtained from the Koç University Biomedical Research Ethics Committee (2025.258.IRB2.124; Date: July 31, 2025). In addition, institutional permission will be obtained from Koç University Hospital for this study. Participation of the participants in the study will be voluntary. Patients and their relatives will be informed about the study, and written informed consent will be obtained from patients who agree to participate. Participants will be able to leave the study at any time without any justification. No incentive will be given for participation. Only the research team will have access to the collected data. The data will be used for research purposes only, and appropriate security measures will be taken to ensure that it is not shared with third parties. In the AINurse training program, only the patient's first name will be identified, and surname and other identifying information will not be used.

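### Two ICUs are pooled under unstratified simple randomisation with an unadjusted comparison, so the length-of-stay hypothesis (H3) loses precision and is exposed to chance imbalance by unit

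*Protocol*

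**What the plan says.** - **Units.** Setting, Participants, and Sample Size says that the general ICU "has 16 beds and the cardiovascular surgery intensive care unit (CVSICU) has eight beds". It puts yearly volume at "a total of 1950 patient admissions annually, 1500 in the NICU, and 450 adult patients in the CVSICU". NICU appears nowhere else in the protocol; the sentence before names the general unit GICU.
- **Pooling.** Under Data Collection and Follow-up, "randomization will be performed among patients hospitalized in the intensive care unit and the cardiovascular surgery intensive care unit". No separate list per unit is mentioned.
- **Method.** Recruitment, randomisation, and blinding states that "a computer-assisted simple randomization method will be employed". Neither stratification nor blocking is mentioned. The reason given is: "This approach aims to minimize selection bias and control for potential confounding variables". The means it offers is that each patient has the same chance of either arm.
- **Outcome.** H3 is that AI-nurse patients "will have shorter lengths of stay in the intensive care unit than patients who receive the Human Nurse orientation training".
- **Analysis.** Data Analysis names a t-test, or a Mann-Whitney U test if the data are not normal. It gives no term for unit.
- **Size.** Total N is not fixed. It is to be calculated after a 10-patient pilot.

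**The concern.** A general ICU and a cardiovascular surgery ICU probably differ in case mix and course of stay. Equal assignment probability balances unit on average over repeated trials, but does not secure balance in one trial, least of all a small one. If one arm happens to receive more CVSICU patients and the units differ in stay, the observed H3 difference moves by the imbalance times the gap between units. An analysis without unit also leaves the between-unit variation in the error term. At stake are the power of H3 and the credibility of its estimate if the baseline table shows the units unevenly split.

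**Working it through.** The protocol states no sample size, power or occupancy, so there is no design figure to reproduce. Its one sum is correct: 1500 + 450 = 1950.

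**Step 1. What the bed and admission figures say.** Bed-days available per admission = beds × 365 / admissions. This is a ceiling on mean stay, reached only at full occupancy; mean stay = occupancy × ceiling.

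- General ICU, if NICU means GICU: 16 × 365 / 1500 = 3.89 days.
- CVSICU: 8 × 365 / 450 = 6.49 days.
- Ratio 1.67; gap at full occupancy 2.60 days.

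The gap depends on occupancy, which must be assumed:

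| Occupancy GICU / CVSICU | Mean stay, GICU | Mean stay, CVSICU | Gap (days) |
|---|---|---|---|
| 100% / 100% | 3.89 | 6.49 | 2.60 |
| 80% / 80% | 3.11 | 5.19 | 2.08 |
| 70% / 70% | 2.73 | 4.54 | 1.82 |
| 100% / 60% | 3.89 | 3.89 | 0 |
| 90% / 50% | 3.50 | 3.24 | −0.26 |

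**Step 2. Chance imbalance by unit.** CVSICU share p = 450/1950 = 0.231. With near-equal arms, the SD of the between-arm difference in share is √(4p(1−p)/N): 0.133, 0.109 and 0.084 at N = 40, 60 and 100. Simulating simple allocation, with arm sizes also left to chance, gives:

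| Assumed total N | SD of difference | P(10 points or more) | P(20 points or more) |
|---|---|---|---|
| 40 | 0.135 | 47% | 15% |
| 60 | 0.110 | 37% | 7% |
| 100 | 0.085 | 24% | 2% |

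Not counting differences of exactly 10 points, the middle column is 44%, 35% and 23%. If the arms were instead forced to equal size, it would be 57%, 44% and 29%.

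**Step 3. Effect on the H3 estimate.** Shift = imbalance × gap. At the 2.60-day gap, 10 points move the difference in mean stay by 0.26 day and 20 points by 0.52 day. The 95% range, 1.96 × SD (formula) × 2.60, is ±0.68 day at N = 40, ±0.55 at 60, ±0.43 at 100 and ±0.30 at 200. At a gap of zero the shift is zero.

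**Step 4. Cost in precision.** Between-unit variance = p(1−p) × gap² = 0.231 × 0.769 × 2.596² = 1.196. Ignoring unit inflates the sample size by 1 + 1.196/SD², where SD is the within-unit SD (assumed). For an assumed 1-day effect, 80% power and two-sided 0.05:

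| Within-unit SD (days) | Inflation | n per arm, unit ignored | n per arm, unit used |
|---|---|---|---|
| 2 | 1.30 | 82 | 63 |
| 3 | 1.13 | 161 | 142 |
| 4 | 1.07 | 270 | 252 |
| 5 | 1.05 | 412 | 393 |

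At the 1.82-day gap the between-unit variance is 0.586 and the inflation falls to 1.15 (SD 2) and 1.02 (SD 5).

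**Step 5. Type I error.** With simulated log-normal stays (CV 0.8 assumed, 2.60-day gap, equal arms, N = 40 to 100), overall type I error was 0.042 to 0.046 for the t-test and 0.046 to 0.050 for Mann-Whitney. Among trials with an imbalance of 20 points or more it was about 0.065 to 0.113.

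**The case against.** Simple randomisation is a valid method. Chance imbalance by unit is ordinary sampling error, already carried by the unadjusted standard error, and overall type I error stays at or below nominal. At N = 60 with within-unit SDs of 3 to 5 days, even the 2.60-day gap leaves unit explaining only about 12% to 5% of the variance in stay, and a 0.26-day shift is about 0.3 to 0.2 of a standard error. A separate SAP could add unit as a covariate. The sentence on confounding states an aim, not a guarantee. All of this stands, and it limits the point to precision and conditional imbalance.

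Two stronger readings are tempting and should not be drawn:

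- A reader might infer from the bed and admission counts that the two units have very different stays. The counts give ceilings, not means. The gap needs similar occupancy, which the protocol does not give, and it vanishes when CVSICU occupancy is 60% of the GICU's. It also rests on reading NICU as the general ICU. The counts cover all admissions, whereas eligible patients need at least 24 hours in ICU, RASS −1 to +1 and no sedatives. Neither the gap nor the 23% share is known for them.
- A reader might infer that H3 will be biased. It will not be: the shift is random, with mean zero over repeated randomisations.

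The objection does not remove the point. The allocation method is fixed in this protocol, and an SAP cannot restore balance after patients have been allocated. An SAP covariate would recover most of the precision, but no such term is stated here. For H1, no figure suggests that delirium risk differs by unit, so nothing is claimed.

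**Conclusion.** The point holds as one of efficiency and robustness, not validity. A plausible predictor of H3, known before randomisation, is used neither in allocation nor in the stated analysis. The imbalance probabilities in Step 2 rest on the assumed totals and on eligible patients having the same 23% CVSICU share as all admissions. The precision loss of about 5% to 30% rests on the 2.60-day gap, a 1-day effect and within-unit SDs of 5 to 2 days; it shrinks with a smaller gap and is nil if the units do not differ. The unit-driven shift also shrinks as N grows. The change is worth making because it costs little, not because the trial is unsound without it.

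**What to change.** 1. Stratify randomisation by unit (GICU or CVSICU), with a separate list per unit in permuted blocks of varying size. The statistical expert already assigned makes the lists and withholds the block sizes from the researcher.
2. Include unit in the comparison of arms, as a stratified or adjusted analysis. Stratifying the allocation without this gives balance, but the reported standard error would not reflect the gain.
3. Reword the rationale: equal probability balances confounders on average, and stratification is what secures balance on unit.
4. Correct or explain the NICU label.

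The cost is two lists instead of one and one added term in the analysis, with no extra patients or staff. The downside is some predictability from blocks where the person delivering the sessions knows the arm; varying and withholding block size keeps it low. If that is still not acceptable, keep simple randomisation and adjust for unit. This recovers most of the precision but does not guarantee balance.

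### Randomisation is forwarded to the researcher with no step that hides upcoming assignments, and equal probability alone does not secure the stated aim of minimising selection bias

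*Protocol*

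**What the plan says.** Under *Recruitment, randomisation, and blinding*, the Protocol specifies computer-assisted simple randomisation from a public random-number website. On handling, it says: "The randomization process will be performed by a statistical expert other than the researcher and will be forwarded to the researcher". It then gives the purpose, "This approach aims to minimize selection bias and control for potential confounding variables", and the means, "by ensuring equal probability of assignment to either the intervention or control group". The section describes no concealment procedure.

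Entry depends on bedside scores. The inclusion criteria are CAM-ICU 0-2, RASS -1 to +1 and "Glasgow coma scale score of 13-14-15 points". *Data Collection Instruments* states "In the initial stage, patients will be screened for the presence of delirium using the CAM-ICU", adds RASS scoring, and says that "eligibility for study inclusion will be determined based on these scores". It does not name the scorer.

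*Data Collection and Follow-up* places randomisation after written consent, among patients who meet the inclusion criteria. It then describes CAM-ICU and RASS scoring as the first stage, followed by baseline forms completed by the researchers.

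Researchers deliver both arms (*Study Intervention*, Phase 4). Of the AI-Nurse arm it says "This intervention will be implemented by the same researcher over a three-day period", and of the comparator "In the control group, the structured orientation training will be given face-to-face by the Human-Nurse researcher".

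**The concern.** Selection bias at entry has two possible routes: an unfair sequence, or knowledge of the next assignment by someone who can influence who enters. Equal probability closes the first route only. The Protocol presents it as the means to the whole aim, while sending the randomisation output to the study's own researcher without saying in what form or at what moment.

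If a person who recruits or scores can see the next arm, a patient near a CAM-ICU, RASS or Glasgow threshold can be scored in, scored out or deferred according to that arm. The same applies to judged exclusions such as psychiatric illness or impaired brain function. The arms are visibly different (headset against face-to-face), so allocation can be hidden only up to enrolment. That makes concealment at entry the safeguard still available. Selective entry cannot be reliably repaired in the analysis.

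**Working it through.** **Plan figure to reproduce.** There is none. The Protocol fixes no sample size (it is to be calculated after the pilot) and gives nothing that measures this bias. The check is mainly a reading of the text.

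**1. Does equal probability hide the next arm?** Under simple 1:1 randomisation each assignment has probability 0.5. If the list is hidden, the recruiter guesses the next arm correctly with probability 0.5. If the recruiter holds the list, the next arm is known with probability 1. The assignment probability is 0.5 in both cases, so it cannot be what separates a concealed trial from an unconcealed one.

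**2. What the safeguards cover.**

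| Feature in the Protocol | What it protects | What it leaves open |
|---|---|---|
| Expert separate from the researcher generates the sequence | Manipulation of the sequence | The output still goes to the researcher |
| Simple randomisation, no blocks | Guessing from past assignments | Disclosure of the list itself |
| Randomisation after consent, among eligible patients | Entry, if each assignment is drawn and sent at that point | A list drawn and sent earlier also fits the text |

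**3. Is the order of steps clear?** *Recruitment, randomisation, and blinding* assigns eligible participants, and *Data Collection Instruments* puts scoring in the initial stage. Both favour scoring before allocation. *Data Collection and Follow-up* mentions randomisation first and CAM-ICU and RASS scoring afterwards. The order is ambiguous rather than plainly wrong.

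**4. Who could be exposed?** The named recipient is the researcher. Researchers complete the baseline forms and deliver both arms. The recruiter and the eligibility scorer are not named, so overlap with the recipient is possible but not stated.

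**5. Illustration of size. Every input is assumed; none comes from the Protocol.** Let f be the share of assignments foreseen. When one is foreseen, the worst-prognosis fraction q = 10% of candidates is passed over, for one arm a share d of the time and for the other arm a share 1-d. Prognosis correlates r = 0.5 with outcome, and n = 50 per arm.

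- Mean prognosis of an arm steered at rate p is p·φ(z_q)/(1 - p·q), with φ(z_0.10) = 0.1755, and p = f·d or f·(1-d).
- Shift = r × difference between arms. Noncentrality = shift × √(n/2). The test is a two-sided 5% t-test.
- f = 1, d = 1: 0.1755/0.90 = 0.195; shift 0.5 × 0.195 = 0.097 SD; noncentrality 0.097 × 5 = 0.49; false-positive rate 7.7%.
- f = 0.5, d = 1: 0.0877/0.95 = 0.092; shift 0.046 SD; rate 5.6%.
- f = 0.25, d = 1: shift 0.022 SD; rate 5.1%.
- f = 1, d = 0.75: rate 5.7%. With d = 0.5 (no consistent direction): 5.0%.
- f = 1, d = 1, with r from 0.3 to 0.7: 6.0% to 10.4%.

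The effect is small unless foreknowledge is wide and steering runs consistently one way.

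**The case against.** The strongest reply is that this is silence, not a shown fault. The Protocol does not say that a full list is sent, that anything is sent in advance, or that the recipient screens patients. Harm would need all of these: advance disclosure, overlap between recipient and screener, and steering in a consistent direction. A plausible reading of the randomisation and data-collection sections together is that the expert draws and forwards one assignment for each consented, eligible patient, which would conceal the next arm. The sentence on selection bias is worded as an aim, and unpredictable equal-probability assignment does contribute to it.

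Much of this stands. A reader might infer that the researcher holds the whole list while recruiting, or that patients are randomised before eligibility is scored. The documents support neither inference. The first is permitted by the text but not stated, and two sections point against the second. Nor can the illustrative error rates be read as the expected bias in this trial.

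What does not stand is that the existing text is enough. The moment at which randomisation is performed for a patient is not the moment at which the assignment becomes knowable: a list forwarded beforehand complies with every sentence. Independent generation does not protect entry once the output is handed over. Nor is this a matter to leave to a statistical analysis plan, because how assignments reach those who enrol is trial conduct.

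**Conclusion.** The concern holds as a gap in a stated procedure: forwarding the randomisation to the researcher, with equal probability as the named protection, does not secure the stated aim. Concealment is unsecured, not shown to be broken.

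The size of any bias cannot be derived from the Protocol, and the illustrative figures do not carry the conclusion. It rests on the design argument: scored entry criteria, researchers who complete the baseline forms and deliver both arms, visibly different interventions, and a bias that analysis cannot reliably undo. The change should be made because it is nearly free. The safeguards already present keep this short of a critical defect.

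**What to change.** **Replace the forwarding sentence** under *Recruitment, randomisation, and blinding* with:

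*A statistical expert other than the researcher, with no role in recruitment, screening, treatment or assessment, will generate and keep the allocation list and will release one allocation at a time (by message or sequentially numbered opaque sealed envelope), only after consent, confirmation of all inclusion and exclusion criteria, and the baseline forms, CAM-ICU and HADS have been recorded. No one who recruits, screens, treats or assesses patients will see the list.*

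**Amend the selection-bias claim** in the same section to say that random assignment together with concealment of upcoming assignments aims to minimise selection bias.

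**Reorder *Data Collection and Follow-up*** to match: consent; scoring and confirmation of eligibility; baseline measures; allocation; first session.

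**Cost.** Protocol wording, and one message per patient from the expert already named or a set of envelopes prepared in advance. No new visits or measurements are needed. The expert must be reachable at enrolment unless envelopes are used, and consent, scoring, baseline measures and release must be finished before the patient's first 10:00 session.
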